## BACKGROUND

Identification of the epidural space involves recognition of a change in pressure from one tissue plane to another. This drop of pressure, called “loss of resistance” (LOR), across a band of connective tissue into the epidural space is detected using a needle-syringe apparatus. The operator applies pressure to the plunger of the syringe until the drop in pressure is identified when the plunger collapses. The epidural catheter, a small tube that is inserted into the epidural space to give the medication, is then advanced using the needle as a guide. Confidence in locating the epidural space is based on clarity of the loss of resistance and the ease of threading the epidural catheter.

When there is difficulty in advancing the epidural catheter after the epidural space has been identified, several maneuvers are performed in order to correct the problem. These include: injecting saline through the needle to “expand” the epidural space, advancing the needle tip 1-2 mm, inserting a new flexible epidural catheter, inserting a new non-flexible epidural catheter, rotating the needle bevel, changing a patient’s posture, pulling the needle back to re-engage the *ligamentum flavum* and then performing a second LOR technique, and removing the needle entirely and performing a new placement at the same or different interspace (1). Each time a new maneuver is performed, this is considered a new attempt at threading the epidural catheter into the epidural space. Not succeeding on threading the epidural catheter correctly into the epidural space on the very first try is considered a “failure to thread,” however these maneuvers are performed until adequate labor analgesia is established in all patients. Establishing labor analgesia on the first epidural catheter threading attempt reduces the amount of time between when the epidural is requested and when pain relief is administered. A “more successful”

epidural threading attempt is related to a decrease in the time required to thread the epidural and adequately relieve labor pain.

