## **OBJECTIVES**

The aim of the study is to assess if there is a difference in ability to thread the epidural catheter (measured in time to thread) from two different pain management kits: Arrow® and B.Braun®. In order to improve patient care at U of M, if there is a difference in the time to thread epidurals with one kit over the other (i.e. one epidural catheter threads more easily than the other), we would like to use the kit with decreased time to thread in the future. We would like to make this comparison based on data.

Our hypothesis is that there is no difference in the average time required for clinicians to thread the epidural catheters from the Arrow® and B.Braun® pain management kits.

The primary outcome is to compare the number of epidural threading attempts between the Arrow® and B.Braun® pain management kits.

Secondary objectives of this study are to compare the difference in average time required to advance the epidural catheter, the number of epidural needle manipulations once the epidural space has been established, the incidence of unintended dural punctures, the incidence of paresthesia, and the incidence of epidural intravascular cannulations between the two different kit vendors.

Our findings may not be generalizable to other facilities due to local practices (presence or absence of trainees, training level of the residents, obesity of patients, etc.) but data will be made publically available. This project is primarily intended to improve patient care at U of M via scientific level analysis.

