Once, the epidural catheter has been threaded successfully, the clinician will apply negative pressure to the catheter through a syringe in order to rule out blood or cerebro-spinal fluid (CSF) aspiration. If aspiration of blood and CSF is negative, the patient will be given our standard medications consisting of 2 ml Lidocaine 1.5% with epinephrine 1:200,000 to rule out intrathecal catheter placement. Following 2 minutes, the patients will be given additional 3 ml from the lidocaine and epinephrine mixture in order to rule out intravascular cannulation. In addition, a standard loading bolus of bupivacaine 0.125% with fentanyl 3 mcg/ml will be administered in three fractionated doses of 5 ml each, through an epidural pump. All patients will be then connected to a programmed intermittent epidural bolus pump with the following settings: bupivacaine 0.125% with fentanyl 3 mcg/ml, programmed intermittent bolus 6 ml every 45 minutes. Patient's demand bolus 6 ml every 15 minutes, without baseline infusion.

If the epidural catheter cannot be sufficiently advanced into the epidural space, one or more of the following maneuvers will be adopted: additional saline will be administered through the Tuohy needle; alternatively, a new flexible epidural catheter can be inserted; if the catheter advances following one of these afore-mentioned maneuvers, the thread will be considered successful with minor adjustments. Conversely, if the needle is rotated, re-angled, redrawn and

re-advanced or advanced blindly, these will all be considered as major needle manipulations and recorded as failure of that attempt to advance the epidural catheter. Further attempts are made until proper epidural analgesia is established.

Establishment of successful labor analgesia will be defined at a verbal analogue score equal to or less than 10 on a 100-point scale within 30 min from the standard epidural medication administration. All data related to the technical aspects of the epidural placement will be collected in the form shown in the appendix. The goal of both study groups is the management of labor pain.

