### *Statistical Analysis*

Statistical analysis will be performed using SAS 9.3 (SAS Institute, Cary, NC). The

primary outcome will be the success rate of epidural catheter threaded with each epidural kit, which will be compared by group using a chi-square test or Fisher's exact test, as appropriate. The secondary outcomes will be analyzed as follows: the difference in number of epidural attempts will be compared using the Mann-Whitney test; the difference in time to perform the epidural start to finish defined as the time the epidural needle is inserted through the patient's skin to the end of the catheter thread will be compared using the Student's t-test; the difference in the incidence of epidural needle manipulations once the epidural space has been established will be compared using the Chi-Square or Fisher's exact test, as appropriate; the difference in incidence of unintended dural puncture, paresthesia, and intravascular cannulations will be compared using the chi-square or Fisher's exact test, as appropriate. In addition, the difference in unsatisfactory labor analgesia with Arrow® and B.Braun® kits will be compared through the chi-square or Fisher's exact test, as appropriate, by looking at the difference in percentages of patients who have a verbal analogue pain score equal or less than 10 (scale 0 to 100) at 30 minutes following epidural medication administration. A p-value of 0.05 throughout will be considered statistically significant.

All statistical analyses will be performed using SAS 9.3 (SAS Institute, Cary, NC).

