**Table 3 Success rates and complications of corrective maneuvers performed**

Maneuver	Single-orifice		Multi-orifice		Statistics
	Success (%)	Complications	Success (%)	Complications	
Saline injection	x/X (x%)	X	x/X (x%)	X	p=
Rotate needle bevel	x/X (x%)	X	x/X (x%)	X	p=
New placement	x/X (x%)	X	x/X (x%)	X	p=
Re-engage ligament, re-advance	x/X (x%)	X	x/X (x%)	X	p=
Advance needle	x/X (x%)	X	x/X (x%)	X	p=
Change needle angle	x/X (x%)	X	x/X (x%)	X	p=
New catheter	x/X (x%)	X	x/X (x%)	X	p=

Data are number (%).

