# SINGLE vs MULTI-ORIFICE CATHETER STUDY FORM

ANESTHESIOLOGIST CODE \_\_\_ Date \_\_\_ Time \_\_\_ room \_\_\_

Anesthesiologist : Attending Fellow CA-3 CA-2 CA-1

Patient Description Age: \_\_\_ Gest Age: \_\_\_ Ht/Wt: \_\_\_ G \_\_\_ P \_\_\_

Cervical dilation \_\_\_ cm Estimated Level of placement: L \_ - L \_

Relevant patient's comorbidities: \_\_\_\_\_

EPIDURAL KIT: ARROW BBRAUN

Time: loss of resistance to Epidural needle removed following successful placement \_\_\_ minutes : \_\_\_ seconds

Loss of Resistance Unable to get Loss Equivocal Loss Clear Loss

Dural Puncture epidural used ? YES NO

If Dural Puncture Epidural used, CSF in the spinal needle? YES NO

Dural Puncture Epidural used because of:  Equivocal loss  As part of technique

Because catheter wouldn't thread and wanted to make sure I was midline

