## Ease of Threading the Epidural Catheter

- |   |                              |
|---|------------------------------|
|  Easy thread without further maneuvers  |                              |
|  hydrodissection, then catheter:  | Thread Did not thread |
|  new catheter from the same brand, then catheter:   | Thread Did not thread |
|  Rotated the needle, then catheter:   | Thread Did not thread |
|  Changed needle angle, then catheter:   | Thread Did not thread |
|  Withdrawal and re-advanced the needle with an additional LOR (this count as an additional attempt), then catheter: | Thread Did not thread |
|  Advanced the needle blindly, then catheter:  | Thread Did not thread |
|  Changed space  |                              |

Patient Comfort at 30 minutes (VAS  $\leq$  10/100) YES NO

Additional Number of attempts after loss of resistance 0 1 2 3 4 5

Complications (circle all that applies)

Wet tap Paresthesias Intravascular Other (please explain)

Epidural analgesia failed and then epidural Replaced? YES NO

Delivery date \_\_\_ and Time \_\_\_\_\_

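### The threading-failure rule does not mention abandoning a placement because the catheter would not thread, and the form's changed-space box records neither result nor reason, so such cases cannot be reliably classified

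*Combined protocol and SAP*

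**What the plan says.** Statistical Analysis makes the outcome binary: the "primary outcome will be the success rate of epidural catheter threaded with each epidural kit", compared by chi-square or Fisher's exact test. It does not define success. (Objectives differs: "The primary outcome is to compare the number of epidural threading attempts".)

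The sorting of rescue manoeuvres is in Equipment, Technique and Study Data Collection:

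- **Success with minor adjustments:** more saline, or a new catheter, after which the catheter advances.
- **Failure:** "Conversely, if the needle is rotated, re-angled, redrawn and" re-advanced, or is pushed forward blindly; "these will all be considered as major needle manipulations and recorded as failure of that attempt to advance the epidural catheter".

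The Background lists more rescue manoeuvres, including "removing the needle entirely and performing a new placement at the same or different interspace". It calls any lack of success on the first try a failure to thread. Study Size plans on the same idea, the proportion not threaded at the first attempt. Table 3 has a row for "New placement", separate from its row for re-engaging the ligament.

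On the form, each rescue line under Ease of Threading carries a threaded / did not thread result except the last, "Changed space". Elsewhere the form has one loss-of-resistance item (unable, equivocal, clear), a count of further attempts after loss was obtained, and a reason for using a dural puncture epidural: "Because catheter wouldn't thread and wanted to make sure I was midline".

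**The concern.** A provider finds the epidural space, cannot thread, takes the needle out and succeeds at another interspace. This is a plain first-try threading failure, yet the Methods list does not name it and the form gives it a bare tick. The same tick is correct when loss of resistance was never found, which says nothing about how the catheter threads. A new placement at the same interspace has no box of its own.

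Whoever derives the primary outcome must then decide case by case, after the fact and in an open-label comparison, whether a ticked box means failure. Either blanket choice misclassifies: ignoring the tick loses true failures, and counting every tick adds cases where threading was never tested. The planning rates imply very few failures, so a handful of uncertain cases could matter to the comparison of kits.

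**Working it through.** **1. Where each event is classified**

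| Event after loss of resistance | Methods rule | Form | Table 3 row |
|---|---|---|---|
| Saline; new catheter | success, minor adjustment | box with result | yes |
| Rotate; re-angle; withdraw and re-advance; advance blindly | failure | box with result | yes |
| New placement, different interspace | not named | box, no result, no reason | yes |
| New placement, same interspace | not named | no box of its own | yes (same row) |
| Dural puncture because the catheter would not thread | not named | reason tick-box | no |

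**2. Can other fields recover the third and fourth rows?** Only in part.

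- The loss-of-resistance item appears once and is not tied to a space. A clear loss may describe the abandoned placement or the one that worked.
- The count of further attempts is limited to those after loss of resistance. The note that a manoeuvre counts as an additional attempt is attached to withdrawal and re-advance, not to changing space.
- The Methods count each skin wheal as an attempt, but the form has no wheal count, and a new wheal can also follow a loss never found.

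A clear loss with a changed space and at least one further attempt suggests a threading failure. It does not record one.

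**3. The plan's own figure.** Inputs from Study Size: 11% and 1% not threaded at first attempt, 80% power, alpha 0.05 (taken as two-sided). The mean rate is 0.06 and the difference is 0.10.

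n = [1.96·√(2·0.06·0.94) + 0.8416·√(0.11·0.89 + 0.01·0.99)]² / 0.10² = (0.6583 + 0.2763)² / 0.01 = 87.3

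With continuity correction: (87.3/4)·[1 + √(1 + 4/(87.3·0.10))]² = 106.4, so 107 per group. This matches the plan. It assumes that every first-attempt failure is counted.

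**4. What uncounted failures would cost (illustration only).** At 120 per kit, 0.11 × 120 = 13.2 and 0.01 × 120 = 1.2, so about 13 v 1. The 1% review does not name its kit; giving the two rates to the two kits is an assumption. Suppose some of the 13 were abandoned placements and were scored as successes. Two-sided Fisher's exact test against 1/120:

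| Failures counted | Uncounted | Observed rate | p |
|---|---|---|---|
| 13 | 0 | 10.8% | 0.0014 |
| 10 | 3 | 8.3% | 0.010 |
| 8 | 5 | 6.7% | 0.036 |
| 7 | 6 | 5.8% | 0.066 |
| 6 | 7 | 5.0% | 0.12 |

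In power terms, if the same share of failures went uncounted in both kits, continuity-corrected power at 107 per group would fall from 80% to 75%, 68% or 60% for shares of 10%, 20% or 30%. The documents give no share.

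**The case against.** The strongest reply is that the plan already settles these cases. The Background calls any first-try miss a failure to thread, names a new placement among the manoeuvres, and treats each manoeuvre as a new attempt; Study Size uses the same first-attempt idea. The Methods list never says it is exhaustive, and a needle taken out and placed elsewhere has, in ordinary words, been redrawn and re-advanced. The form's easy-thread box excludes further manoeuvres, so ticking it together with a changed space would be a recording error. Under the Objectives' version of the primary outcome, a new wheal adds an attempt.

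Much of this stands. A reader might infer that the most complete failures drop out of the primary outcome, or are scored as successes. The documents do not support that: no rule does either, and the Background points the other way. A reader might also infer that the comparison would lose significance. That needs 6 of 13 failures to be both abandoned placements and scored as successes, and nothing in the documents supports such a share. Nor do they show that rescue choices are alike in the two kits, so a bias towards no difference is plausible but not established.

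The reply does not close the gap. The Background's first-try definition cannot simply override the Methods, because it would make saline and a new catheter failures where the Methods call them successes. Table 3 and the form list re-advance and new placement separately, which leaves a coder unsure whether one term covers both. Above all, a general definition cannot supply a reason that was not written down at the bedside.

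A reader might further infer that a dural puncture prompted by a catheter that would not thread should itself count as failure. The form describes it as a midline check. What follows may be saline or a new catheter, which the Methods call a success, so automatic scoring as failure is not supported.

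**Conclusion.** The point holds as a gap in classification and recording. An abandoned placement due to non-threading is missing from the Methods list. The form records it without result or reason, and the remaining fields identify it only indirectly. The binary primary outcome is therefore not reliably derivable for these cases, and the Table 3 success rate for new placement has no direct source field.

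The number of cases affected is unknown and could be very small. The p-values above show only that, with about 13 v 1 expected failures, five or six uncounted cases would be enough to move the result from clear to borderline. They rest on the planning rates, on assigning those rates to the two kits, and on an assumed number of cases scored as successes. The change is worth making because it is nearly free now and the reason cannot reliably be recovered later.

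**What to change.** **Protocol, Equipment, Technique and Study Data Collection.** Add one sentence: a new placement or changed interspace, made after loss of resistance because the catheter did not thread, is recorded as a threading failure. This agrees with the first-try wording in the Background and Study Size.

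**Form.** Widen the last Ease of Threading line to cover a changed space or a new placement. Give it a threaded / did not thread result and a reason: no loss of resistance, or catheter would not thread. Count only the second reason as a threading failure.

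**Dural puncture for a catheter that would not thread.** Do not score it as failure automatically. Classify the case by the manoeuvre that then allowed threading, and reconcile the Background, the Methods rule and Statistical Analysis on this point.

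**Cost.** One sentence and two tick-boxes on a short form, and possibly a slightly higher observed failure rate in both kits. No extra patients or procedures are needed. The planned sample size stays as it is, since the 107 per group already assumes that all first-attempt failures are counted.

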### *Study Size*

In order to determine the study size, we looked at 114 consecutive epidural placements as part of our routine quality assurance with the Arrow® Epidural Catheterization Kit at Von Voigtlander. We found that in 11% (n=12) of epidurals placed, the epidural catheter did not thread on the first attempt. In a separate quality assurance check we retrospectively reviewed 100 epidural placements finding out that in 1% (n=1) of epidurals placed, the epidural catheter did not thread on the first attempt. A sample-size analysis for the primary outcome shows that 107 epidural placements per group would provide a power of 80% to detect a difference in proportion between the two techniques of 0.10 at the 0.05 level. Considering an attrition of 10-20% for follow-up and data missing, a total number of 240 epidural placements will be collected. Power calculations were computed using PASS 14.

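### The primary endpoint is scored inconsistently: the trial is sized on first-attempt failure per placement, but the scoring rules let a placement whose first attempt failed count as a success

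*Combined protocol and SAP*

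**What the plan says.** All references are to the combined protocol and SAP.

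- **Background.** Failure to thread means not succeeding on the very first try, and every new manoeuvre counts as a new attempt. The manoeuvres listed there include saline injection and a new catheter. The section adds that "these maneuvers are performed until adequate labor analgesia is established in all patients".
- **Objectives.** The primary outcome is the number of threading attempts.
- **Equipment, Technique and Study Data Collection.** An attempt is a skin wheal, or a withdrawal of the needle with a repeat loss of resistance. For saline or a new catheter, "if the catheter advances following one of these afore-mentioned maneuvers, the thread will be considered successful with minor adjustments". For a needle that is rotated, re-angled, withdrawn and re-advanced, or advanced blindly, the event is "recorded as failure of that attempt to advance the epidural catheter. Further attempts are made until proper epidural analgesia is established".
- **Study Size.** For the Arrow series of 114: "We found that in 11% (n=12) of epidurals placed, the epidural catheter did not thread on the first attempt". For a second series of 100, whose kit is not named: "finding out that in 1% (n=1) of epidurals placed, the epidural catheter did not thread on the first attempt". The target is a "difference in proportion between the two techniques of 0.10 at the 0.05 level".
- **Statistical Analysis.** The "primary outcome will be the success rate of epidural catheter threaded with each epidural kit", compared by chi-square or Fisher's exact test as appropriate.
- **Study form and tables.** The form records whether the catheter threaded after each manoeuvre, major ones included, and has no placement-level success field. Table 3 has a success column for major manoeuvres. Table 2 reports catheter failure to advance as a count and percentage under a group N.

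**The concern.** The endpoint that was sized and the endpoint that is scored are not tied together. The first is a single yes/no per placement, decided on the first attempt. The second comes from rules that attach failure to an attempt, allow attempts to continue, and never convert the sequence into one result per placement.

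The sections also disagree about minor manoeuvres. A placement that threads after saline alone is a first-try failure under the Background and a success under the Technique section.

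Both gaps act in the same direction: some placements that count as failures in the sizing can count as successes in the analysis. If that happens in both kits, both failure rates fall, the difference between them shrinks, and power falls with it. The study is open label, so a scoring rule left to be settled after the data are seen is also open to influence from knowledge of the kit.

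**Working it through.** **1. The plan's own figure.** Inputs from Study Size: p1 = 0.11, p2 = 0.01, difference d = 0.10, alpha 0.05 (two-sided assumed), power 80%. The mean rate is 0.06.

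- Uncorrected: n0 = [1.960·√(2·0.06·0.94) + 0.842·√(0.11·0.89 + 0.01·0.99)]² / 0.10² = (0.658 + 0.276)² / 0.01 = 87.3, so 88 per group.
- With continuity correction: n = (n0/4)·[1 + √(1 + 4/(n0·d))]² = (87.3/4)·(1 + √1.458)² = 106.4, so 107 per group.

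The stated 107 is reproduced. The arithmetic is sound, but it belongs to a first-attempt failure counted once per placement.

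**2. The rules applied to four possible placements.**

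| Sequence after first loss of resistance | Background (first try) | Technique section |
|---|---|---|
| Saline, threads | Failure | Success |
| Rotation, does not thread; saline, threads | Failure | Failed attempt under one rule, success under the other |
| Withdrawal with repeat loss of resistance, then threads | Failure | One failed attempt, then a thread; placement result not stated |
| Saline, does not thread; rotation, threads | Failure | Failed attempt; placement result not stated |

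Rows 2 and 4 use the same two manoeuvres. Only row 2 meets the success rule, because of which manoeuvre came last. In row 1 the two sections contradict each other outright.

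**3. What rescoring would do.** Let f be the share of first-attempt failures that end up scored as successes. The documents give no value for f, and I assume it is equal in both kits. The rates become 0.11(1−f) and 0.01(1−f), and the difference becomes 0.10(1−f). Power is exact, obtained by summing the two binomial distributions over all tables with two-sided p ≤ 0.05, at 120 per kit.

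| f | Rates | Difference (points) | Fisher | Chi-square, uncorrected |
|---|---|---|---|---|
| 0 | 11% v 1% | 10 | 91% | 95% |
| 1/4 | 8.25% v 0.75% | 7.5 | 77% | 86% |
| 1/3 | 7.33% v 0.67% | 6.7 | 70% | 81% |
| 1/2 | 5.5% v 0.5% | 5 | 48% | 68% |

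The plan leaves the choice of test open. If chi-square were used whenever the expected counts reach 5 (my assumption), power would be 81%, 72% and 49% for the three shares. At 107 per kit, Fisher power is 87% with no rescoring and 70%, 62% and 40% for the three shares.

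**The case against.** The strongest reply is that the intended endpoint can be read from the rest of the document. The Background ties failure to the first try, Study Size counts first-attempt failures among placements, and the Table 2 shell shows one failure count per group out of the placements. The Technique section contrasts its two rules, so minor-only and major-only placements fall on different sides, and both rules apply only to mixed sequences. The form already collects most of what is needed, so little is lost for good.

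Much of this stands. It makes the per-placement, first-attempt reading the likelier one, and on that reading the planned contrast is intact. It also rules out two stronger inferences that a reader might draw.

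- **That the contrast disappears**, because every placement is pursued until it works and both kits score 120/120. This needs an analyst to score final threading, which the Background and Study Size sections point away from.
- **That attempts become the denominator.** Study Size and Table 2 use placements, and the number of attempts is a separate secondary outcome in the Statistical Analysis section.

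The reply does not remove the gap. The likelier reading still conflicts with the Technique section over saline and a new catheter. Nothing in the Statistical Analysis section limits success to the first attempt, and mixed sequences are foreseeable because the plan allows one or more manoeuvres.

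**Conclusion.** The point holds as an inconsistency in how the primary endpoint is defined and scored. It is not a sample-size error, since 107 per group is correct for the endpoint that was sized. The documents permit a placement with a failed first attempt to be scored a success, but they do not state that it will be.

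The loss of power cannot be known from the documents. The figures of 77%, 70% and 48% (Fisher) or 86%, 81% and 68% (uncorrected chi-square) at 120 per kit are illustrations. They rest on assumed shares, on equal rescoring in both kits, and on planning rates of 11% and 1%. With a quarter rescored, power stays above 80% by chi-square and falls below it by Fisher, so no firm statement that the trial is underpowered follows.

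Nor can it be assumed that 11% and 1% are rates of major manipulation. If the quality assurance reviews counted every manoeuvre as a new attempt, as the Background does, those rates may include placements that the Technique section calls successes. The matter should be settled before the data are analysed.

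**What to change.** In the Technique and Statistical Analysis sections, define one binary value per placement, with placements as the denominator.

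- **Failure:** any major needle manipulation (rotated, re-angled, withdrawn and re-advanced, advanced blindly) or change of space, after the first loss of resistance and because the catheter did not advance, whatever manoeuvre came last.
- **Success with minor adjustments:** only placements in which minor manoeuvres alone were used.
- **Wording:** attach the failure to the placement instead of to the attempt.

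Then reconcile this with the attempt definitions in the Background and Technique sections, and align the primary outcome named in the Objectives. Confirm that the 11% and 1% were counted under the same definition. If they were not, restate the power for the endpoint actually scored.

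The cost is a few sentences of protocol text and a check of the two quality assurance reviews. The form's tick boxes supply most of the value without needing the order of manoeuvres. The change-of-space box has no result field, so its scoring must be stated, and a single placement-level field would help. No new patients or procedures are needed, and clinical care does not change.
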